### **7.5.8. Intra-articular Injection Procedure**

IA injections will be performed by the assigned injector. The injector may choose the position of the knee (e.g., extended or flexed), the approach for the injection (e.g., medial or lateral) and the numbing agent to be used (e.g., ethyl chloride, subcutaneous lidocaine; IA anesthetics are not allowed) based on standard of care. Sterile technique should be used.

Prior to injection, the index knee should be thoroughly cleansed using a bactericidal solution. The index knee will be aspirated in all cases prior to administration of study medication.

Following attempted aspiration, 5 mL of the reconstituted FX006 will be injected into the synovial space. Refer to the Pharmacy Binder for detailed instructions on how to prepare FX006.

The same needle used for IA injection of the study medication may also be used for synovial fluid aspiration, thereby allowing for a single injection with syringe replacement. The injector will use a 21 gauge or larger needle for injection and aspiration of fluid.

Patients should be advised to avoid strenuous activities or prolonged weight-bearing activities for approximately 24 to 48 hours following the injection and to also maintain a stable lifestyle with regard to physical activity throughout the duration of the study.

In the event that the patient has an immediate reaction (e.g., tenderness, increased pain, swelling, effusion, decreased mobility of the index knee), the patient should be treated according to local clinical guidelines and physician experience (see also Protocol Section Section 8.1.5).

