 Index knee will be assessed for tenderness, heat/redness, swelling, effusion, and Baker's cyst. New clinically significant findings or findings that worsen for the patient's baseline condition should be recorded as AEs.

 Via Central Laboratory.

 Conduct for women of childbearing potential only.

 Patient questionnaires to be completed prior to all other assessments.

 Complete GPAQ at Week 12 only regardless of when and if second dose is given.

 Steps per day will be captured using a measured function device. Patients will be provided with a device at the Screening visit to be worn for at least 7 days prior to Baseline/Day 1 through Week 12. The site will confirm patient compliance with wearing the device to capture steps per day data at each patient visit from Day 1 through Week 12.

 To be completed prior to dosing only if patient is to receive the 2nd dose of FX006.

 Repeat administration may occur at either Week 12, 16, 20, or 24.

 AEs and Concomitant Medications will be captured from Day 1 (post injection) to Week 12 or 24 for patients who only receive a single injection or to Week 52 for patients who receive a second injection or to Early Discontinuation Visit for patients who discontinue the study early.

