### **7.9.13. Treatment Administration**

At Baseline/Day 1 and the week at which the second dose is to be administered (if the patient is eligible to receive a second dose), the following will occur:

- Study medication will be prepared by the pharmacist/coordinator (Refer to the Pharmacy Binder for instructions on how to prepare FX006).
- Synovial fluid will be aspirated from the index knee just prior to administration of study medication (refer to Section [7.9.12](#) for more details of the synovial fluid aspiration).
- The injector/aspirator will perform the IA injection of the study medication (refer to Section [7.5.8](#) for instructions).

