## 8. CLINICAL SAFETY ASSESSMENTS

Safety evaluations will be based on the assessment of AEs occurring after the initiation of study medication on Day 1 through the last study visit. Results of clinical safety assessments are to be recorded in the patient's medical records and transcribed to the appropriate eCRF, including the AE eCRF for clinically significant findings.

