### **8.1.2. Evaluating and Recording of Adverse Events**

At each visit all AEs that occur from the time of treatment and throughout a patient’s study participation that are observed, elicited by the site personnel, or reported by the patient, will be recorded in the source documentation and appropriate section of the AE eCRF and evaluated by an assessor.

Minimum information required for each AE includes type of event, duration (start and end dates), severity, seriousness, causality to investigational medicinal product, action taken, and outcome.

Severity of AEs will be graded by the Principal Investigator using the Common Terminology Criteria for AEs (CTCAE) version 4.0 (refer to the Study Manual or [http://ctep.cancer.gov/protocolDevelopment/electronic\\_applications/ctc.htm](http://ctep.cancer.gov/protocolDevelopment/electronic_applications/ctc.htm)).

For AEs not listed in the CTCAE, the following definitions should be used:

Grade 1	Mild Symptomatic or mild symptoms Clinical or diagnostic observations only Intervention not indicated
Grade 2	Moderate Minimal, local or noninvasive intervention indicated Limiting age-appropriate instrumental activities of daily living (ADL)*
Grade 3	Severe or medically significant but not immediately life-threatening Hospitalization or prolongation of hospitalization indicated Disabling Limiting self care ADL**
Grade 4	Life-threatening consequences Urgent intervention indicated
Grade 5	Death related to AE

\*Instrumental ADL refer to preparing meals, shopping for groceries or clothes, using the telephone, managing money, etc.

\*\*Self care ADL refer to bathing, dressing and undressing, feeding self, using the toilet, taking medications, and not bedridden.

The relationship of the AE to the investigational medicinal product should be specified by the Principal Investigator, using the following definitions:

1. Not Related: Concomitant illness, accident or event with no reasonable association with treatment.
2. Unlikely: The reaction has little or no temporal sequence from administration of the investigational medicinal product, and/or a more likely alternative etiology exists.

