#### 4.10.1. Adverse Events

Adverse events will be coded using the MedDRA (version 19.1) coding system and displayed in tables and data listings using system organ class (SOC) and preferred term (PT).

Analyses of AEs will be performed for those events that are considered treatment-emergent, where treatment-emergent is defined as any AE with onset after the administration of study treatment, or any event that was present at baseline but worsened in intensity through the end of the study.

If the start date/time of an AE is partially or completely missing, the date/time will be compared as far as possible with the date/time of the start of administration of study drug. The AE will be assumed to be treatment emergent if it cannot be definitively shown that the AE did not occur or worsen during the treatment-emergent period (worst case approach). The following general rules will be used:

- If the start time of an AE is missing but the start date is complete, an AE will only be excluded as being treatment emergent if the start date is before the date of study drug administration or if the stop date/time is before study drug administration.
- If the start time and day are missing but the start month and year are complete, an AE will only be excluded as being treatment emergent if the start month/year is before the month/year of study drug administration or if the stop date/time is before study drug administration.
- If the start day and month are missing but the start year is complete, an AE will only be excluded as being treatment emergent if start year is before the year of study drug administration or if the stop date/time is before study drug administration.
- If the start date is completely missing, an AE will be considered treatment-emergent unless the stop date/time is before study drug administration.

Adverse events will be summarized by patient incidence rates; therefore, in any tabulation, a patient contributes only once to the count for a given SOC or preferred term.

Summary tables will display the number and percentage of patients who experienced at least one TEAE in each of the following categories:

- Any TEAE
- Any Serious Adverse Event (SAE)
- Any TEAE leading to study discontinuation
- Any TEAE by severity (grade 1-5)
- Any TEAE by relationship
- Any index-knee related TEAE
- Any index-knee related SAE
- Any index-knee related TEAE leading to study discontinuation

- Any index-knee related TEAE by severity (grade 1-5)

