- Any index-knee related TEAE by relationship
- Any TEAE related to injection procedure

Separate tabulations will be produced for each of following categories:

- All TEAEs by SOC and PT
- All SAEs by SOC and PT
- All TEAEs related to study drug by SOC and PT
- All TEAEs related to injection procedure by SOC and PT
- All TEAEs by maximum severity by SOC and PT
- All TEAEs leading to study discontinuation
- All TEAEs leading to death
- All index-knee related TEAEs by SOC and PT
- All index-knee related TEAEs related to study drug by SOC and PT
- All index-knee related TEAEs by maximum severity by SOC and PT

Summary tables and the tabulation of All TEAEs by SOC and PT will be presented for the following patient groups and time periods, with a separate table for each patient group:

1. Patients receiving only one dose
  - a. First dose to Week 12
  - b. First dose to Week 24 (end of study)
2. Patients receiving the second dose at Week 12
  - a. First dose to Week 12
  - b. Week 12 to Week 24
  - c. Week 12 to Week 52
3. Patients receiving the second dose at Week 16
  - a. First dose to Week 16
  - b. Week 16 to Week 32
  - c. Week 16 to Week 52
4. Patients receiving the second dose at Week 20
  - a. First dose to Week 20
  - b. Week 20 to Week 40
  - c. Week 20 to Week 52
5. Patients receiving the second dose at Week 24
  - a. First dose to Week 24
  - b. Week 24 to Week 48
  - c. Week 24 to Week 52

Summary tables and all tabulations will be presented for the following time periods for patients receiving two doses only (same table):

1. Baseline to Week 52
2. Baseline to Week 12
3. Second dose to 12 weeks after second dose

Date and time of onset of TEAE will be used to assign the time periods.

In the summary table for "Any TEAE by SOC and PT", an additional row with the number of events observed will be presented. A patient will be counted once for the number of patients if they have multiple events. The total number of events will be the absolute number of events observed, and a patient will be counted more than once for the event totals if they have multiple events.

In these tabulations, related is defined as any TEAE deemed possibly, probably or definitely related to study drug by the investigator. If relationship is missing, it will be imputed as related.

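### Adverse event capture and dose periods start at the injection, but aspiration comes first, so events starting in that gap are missed at dose 1 and, if timed, not credited to dose 2

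*Protocol*

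**What the plan says.** **Order of steps.** Protocol 7.5.8 states: "The index knee will be aspirated in all cases prior to administration of study medication". Protocol 7.9.13 gives the same order for both dosing visits: "Synovial fluid will be aspirated from the index knee just prior to administration of study medication". The injector chooses a numbing agent according to usual practice. One needle may serve for both aspiration and injection, with a change of syringe.

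**Start of capture.** Note 17 to Protocol Table 1 reads "AEs and Concomitant Medications will be captured from Day 1 (post injection) to Week 12 or 24". Protocol 8 bases safety evaluation on "AEs occurring after the initiation of study medication on Day 1". Protocol 8.1.2 records "all AEs that occur from the time of treatment". Protocol 7.9.14 has patients monitored for events once they have received study medication.

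**Analysis.** In SAP 4.10.1, "treatment-emergent is defined as any AE with onset after the administration of study treatment"; an event present at baseline that worsens also qualifies. For the dose periods, "Date and time of onset of TEAE will be used to assign the time periods". The planned output includes "All TEAEs related to injection procedure by SOC and PT" and a procedure-related row in the summary tables. No rule treats aspiration or numbing as the start of a dose period.

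**The concern.** Aspiration is an invasive step that the protocol requires, and it also supplies the biomarker samples (Protocol 7.9.12). Harm from it is harm from taking part. The primary objective is the safety and general tolerability of repeat administration, and the SAP plans to report events related to the injection procedure. If capture begins only once drug is in the joint, that reporting leaves out new events that start during aspiration or numbing, such as a faint, a reaction to the numbing agent or bleeding on aspiration (examples only; the documents name none of them).

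The second dose raises a separate question. Capture is already running, so the event is collected, but its onset precedes the second injection. An event caused by the second procedure may then not count for the second dose, although the plan sets first-dose and second-dose event rates side by side.

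**Working it through.** The plan states no figure on this point, so there is none to reproduce. The check follows one new event, with onset after the procedure starts and before drug is injected, through the rules.

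**Dose 1**

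1. Capture: the onset is before the window in note 17, and before the start points in Protocol 7.9.14 and 8. The site is not asked to record it.
2. If recorded with an onset time before the injection: not treatment-emergent unless it worsens later (SAP 4.10.1).
3. If recorded with a date but no time: it stays treatment-emergent, because the missing-time rule excludes it only when the start date, or the stop date/time, is before dosing.
4. Procedure-related events that start after the injection are captured and tabulated as planned.

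**Dose 2**

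The event follows the first injection, so it is recorded and is treatment-emergent. Only the period is in question.

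| Display in SAP 4.10.1 | Re-dosed at Week 12 | Re-dosed at Week 16, 20 or 24 |
|---|---|---|
| Per-group tables, timed event | First-dose period | First-dose period |
| Pooled two-dose table, timed event | Baseline to Week 12 column | Neither 12-week column |
| Pooled two-dose table, full study | Counted to Week 52 | Counted to Week 52 |

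The per-group entries assume that the period boundary is the time of the second injection. The SAP labels these periods by week, and adjacent periods share the dosing week as their boundary. The table of procedure-related events by SOC and PT appears only in the pooled two-dose display; the per-group tables carry the procedure-related summary row.

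The period rule needs an onset time, but the minimum event data in Protocol 8.1.2 are start and end dates. SAP 4.10.1 leaves events whose period cannot be determined out of the period tables, so an untimed dosing-day event may drop out of them.

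**Scale**

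Inputs: 200 planned patients (Protocol 9.3); a second-dose share of 66% as planned (Protocol 9.3), or more than 90% as observed (SAP 5), taken here as 90%.

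- First procedures: 200.
- Second procedures: 200 × 0.66 = 132, or 200 × 0.90 = 180.
- Expected events = n × p, where p is the assumed rate of pre-injection onset per procedure. P(at least one) = 1 − (1 − p)^n.

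| Assumed p | Dose 1 (n = 200) | Dose 2 (n = 132) | Dose 2 (n = 180) |
|---|---|---|---|
| 0.1% | 0.2 | 0.13 | 0.18 |
| 0.5% | 1.0 | 0.66 | 0.9 |
| 1% | 2.0 | 1.32 | 1.8 |
| 2% | 4.0 | 2.64 | 3.6 |
| 5% | 10.0 | 6.6 | 9.0 |

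At p = 1%, the probability of at least one such event is 1 − 0.99^200 = 0.87 at dose 1, and 0.74 (n = 132) to 0.84 (n = 180) at dose 2.

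**The case against.** The strongest reply is that the study drug is the subject of the primary objective, so anchoring events to drug administration is a legitimate choice. The gap is also short: aspiration comes immediately before injection and may use the same needle. Event rates are not formally tested. All of this stands, and it limits the size of the point. It does not explain why a plan that reports procedure-related events should leave out the first part of the procedure.

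A second reply is that Protocol 8.1.2 counts events from the time of treatment, and 7.9.13, headed as treatment administration, lists aspiration among its steps. On that reading aspiration is already inside the window. The reading is possible, but note 17, 7.9.14 and 8 are narrower, and sites would need to be told which applies. Protocol 7.9.5 adds to the doubt, since it sends clinically significant knee findings at the Baseline visit to medical history.

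Three stronger readings are tempting, but the documents do not support them:

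- A reader might infer that procedure events in general are lost at dose 1. Only onsets in the short pre-injection gap are affected, and even those count if they worsen, or if they are recorded without a time and the missing-time rule does not exclude them.
- A reader might infer that every knee is numbed. Only aspiration is specified for all cases; numbing of every knee is at most implied.
- A reader might infer that such events at dose 2 are always credited to the first dose. In the pooled table this is so only for Week 12 re-dosing. For later re-dosing, both 12-week columns leave out pre-injection events, so in that comparison the two doses are not tabulated differently.

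**Conclusion.** The point holds in a narrow form. A new event that starts between the beginning of the injection procedure and the first injection is outside the capture window as written. At the second dose such an event, if timed, is not attributed to that dose. The procedure-related summaries therefore omit or misplace events from part of the procedure.

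The effect is probably small, and the documents give no rate from which to estimate it. The counts shown rest entirely on the assumed rates, on planned rather than actual enrolment, and on onset times being recorded. No stated figure in the plan changes. This is a low-cost improvement and does not threaten the study's conclusions.

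**What to change.** **Protocol** (Table 1 note 17, and Sections 7.9.14, 8 and 8.1.2): start adverse event capture on Day 1 at the start of the injection procedure, meaning aspiration and any numbing before it. Require an onset time for events on dosing days.

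**SAP 4.10.1:** treat an event with onset at or after the start of the procedure at a dosing visit as treatment-emergent, and assign it to the period of that dose.

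**If dosing is already complete:** apply the SAP rule to the dosing-day events that were recorded, and state in the CSR that pre-injection events at dose 1 were outside the capture window.

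**Cost:** one sentence in each place, matching eCRF guidance and one extra time field. A few more events may be reported.

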## 7.9. Study Procedures

### 7.9.1.1. Informed Consent

Prior to initiation of any study related procedures, patients will review and sign the study's informed consent form to participate in the study after having been informed about the nature and purpose of the study, participation and termination conditions, and risks and benefits.

### 7.9.2. Review of Eligibility, Medical History, Prior Treatment, and Medications

Eligibility criteria (inclusion and exclusion criteria), medical history (including OA history), prior treatment and medications are reviewed during screening and again at Baseline/Day 1.

OA medical history includes ACR diagnosis details, OA diagnosis date (if available), K-L grade (See Appendix 1), number of days with index knee pain in the last month, and previous IA steroid or hyaluronic injections.

### 7.9.3. Physical Examination

The physical exam will assess the following body systems:

1. General Appearance
2. Skin
3. Lymphatics
4. HEENT (head, ears, eyes, nose, throat)
5. Cardiovascular
6. Respiratory
7. Abdominal
8. Musculoskeletal
9. Neurological

Any clinically significant findings must be documented in the source and added to the medical history if found at Screening or recorded as an AE if new or worsened from baseline at one of the post-baseline visits.

### 7.9.4. Index Knee X-ray

A diagnostic quality X-ray of the index knee is required (standing, fixed flexion PA view; weight-bearing; use of standardized knee positioning device is required) at Screening and Week 52 (for patients that receive a second injection). The Screening X-ray will be read locally for K-L grading by a radiologist or clinician with rheumatology or orthopedic specialty. In addition, the Screening and Week 52 X-rays will be sent to the central imaging vendor for safety assessments. An image acquisition protocol will be distributed to sites with simple instructions for radio-anatomic positioning for reliable grading.

### 7.9.5. Index Knee Assessment

The index knee assessment will be performed by the designated assessor at the days indicated in Table 1. The index knee will be assessed for tenderness, heat/redness, swelling, effusion, and Baker's cyst. If there is a clinically significant finding outside of the patient's typical disease state at the Screening or Baseline Visit, add to the Medical History. At time points post-baseline, if there are new clinically significant findings outside of the patient's typical disease state or findings that worsen from the patient's baseline condition, record as AEs.

### 7.9.6. 12-lead ECG

At Screening, a 12-lead ECG will be obtained in the supine position. Measures of heart rate, PR interval, RR interval, QT interval, QTc (corrected for Bazett's or Fridericia's) interval and QRS duration will be obtained. If QTc > 450 msec for male patients or > 470 msec for female patients on the first 10-second 12-lead ECG recording, two additional 10-second 12-lead ECG recordings must be collected approximately 1 minute apart. ECGs will be locally read and a copy of each recording will be kept with the patient's source documentation.

### 7.9.7. Vital Signs

Vital signs are to be taken at the days indicated in the Table 1. The following measurements will be taken: sitting blood pressure, heart rate, respiration rate, and temperature.

### 7.9.8. Height, Weight, and BMI determination

Height and weight are to be taken at the days indicated in the Table 1. Height will be measured in centimeters or inches. Weight will be measured in kilograms or pounds. BMI will be calculated using the formulas in Table 2 (reference: [www.cdc.gov](http://www.cdc.gov)):

**Table 2: BMI Calculations**

Measurement Units	Formula and Calculation
Kilograms and meters (or centimeters)	Formula: weight (kg) / [height (m)] With the metric system, the formula for BMI is weight in kilograms divided by height in meters squared. Since height is commonly measured in centimeters, divide height in centimeters by 100 to obtain height in meters. Example: Weight = 68 kg, Height = 165 cm (1.65 m) Calculation: $68 \div (1.65)^2 = 24.98$
Pounds and inches	Formula: weight (lb) / [height (in)] x 703 Calculate BMI by dividing weight in pounds (lbs) by height in inches (in) squared and multiplying by a conversion factor of 703. Example: Weight = 150 lbs, Height = 5'5" (65") Calculation: $[150 \div (65)^2] \times 703 = 24.96$

### 7.9.9. Central Clinical Laboratory Evaluations

Blood samples will be taken at the days indicated in the Table 1. The specific laboratory panels to be run can be found in Table 3. Follow the Central Laboratory Manual for detailed sample collection, handling, storage, and shipping instructions.

**Table 3: Clinical Laboratory Panel**

HEMATOLOGY	CLINICAL CHEMISTRY
Hemoglobin	Sodium
Hematocrit	Potassium
Erythrocyte count (RBC)	Bicarbonate
Mean cell volume	Chloride
Leukocytes (WBC)	Calcium
Absolute counts of:	Total bilirubin
• Neutrophils	Alkaline phosphatase
• Lymphocytes	Alanine aminotransferase
• Monocytes	Aspartate aminotransferase
• Eosinophils	Blood urea nitrogen
• Basophils	Creatinine
• Platelets	Uric acid
INFECTIOUS DISEASES	Total protein
Hepatitis B Surface Antigen	Albumin
Hepatitis C Antibody	Glucose
HIV	
SERUM PREGNANCY TEST (women of child-bearing age only)	
URINE PREGNANCY TEST (women of child-bearing age only) test provided by central laboratory but read locally	

